5. BIOSTATISTICS QUALITY ASSURANCE

Well in advance of study data-lock, programming across all analyses will commence with dummy data. This will allow sufficient time to turn around the 'real' analyses as quickly as possible. Early programming will also allow for a preliminary run at merging of the various datasets into the correct data structure required for analysis. Specifically, the datasets will be taken before data-lock and passed through the necessary biostatistical processes (which will include checking that all the datasets have been imported correctly into SAS and are all able to be correctly merged together).

6. ANALYSIS POPULATIONS

6.1. Intention to Treat

All treatment evaluations will be performed on the principle of 'Intention To Treat' (ITT) unless otherwise specified. The ITT population will consist of all randomised participants regardless of whether they actually satisfied the entry criteria, the treatment actually received, and subsequent withdrawal or deviation from the protocol.

6.2. Per Protocol

A per protocol analysis will also be performed on the primary outcome in order to check the robustness of the results. A per protocol analysis involves looking at the major protocol violations such as cross-over treatments, withdrawals and lost to follow-up. Criteria for defining the per protocol population will include consideration of the following: those who have complied with the treatment allocated, were exposed to the intervention as planned (i.e., used only assigned intervention), were not lost to follow-up, and who do not have major protocol deviations pertaining to eligibility or the assessment of the treatment difference.

7. STATISTICAL ANALYSIS

All statistical analyses will be performed using SAS version 9.4 and R version 3.4.2. Data collected in the NIHI Redcap database will be extracted into SAS for the analyses. All statistical tests will be two-tailed and a 5% significance level throughout the analyses. No adjustments for multiplicity are planned for any of the outcomes.

Summaries of continuous variables which are normally distributed will be presented as means and standard deviations or medians and inter-quartiles for skewed data, while categorical variables will be presented as frequencies and percentages. Continuous variables will be compared with t-tests or Mann-Whitney tests and categorical data with chi-squared tests as appropriate.

A separate EXCEL file containing the SAP tables specific to this study will be provided based on all the analyses stated below (see Appendix I).

All regression analyses will be conducted for the following two comparisons:

- Cytisine plus nicotine e-cigarette group vs Cytisine only group
- Cytisine plus nicotine e-cigarette group vs Nicotine e-cigarette only group

Exploratory analyses will also be conducted comparing the Cytisine only and Nicotine e-cigarette only groups for the primary outcome.

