2.4. Sample size

A sample size of 800 (N=300 in the cytosine group, N=300 in the cytosine plus nicotine e-cigarette group, and N=200 in the nicotine e-cigarette group) will provide 90% power at two-sided $p=0.05$ to detect an absolute difference of 13% in six-month smoking abstinence rates between the combination treatment group and the cytosine group, and 16% difference between the combination treatment group and the nicotine e-cigarette group (taking account of multiple testing).

The predicted difference is based on trial evidence for six month verified continuous abstinence quit rates of 9% for nicotine e-cigarettes, 12% for cytosine, and 25% for combination cessation treatment (averaged). The sample size accounts for a 28% loss-to-follow-up at six months.

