7.5. Primary outcome analysis

The proportion of participants that have been biochemically verified as continuously abstinent at six months by group will be analysed using log-binomial regression, and the risk in each group, relative risks, absolute risk differences, and corresponding 95% confidence intervals will be calculated. All analyses for the

primary outcome will be ITT (unless otherwise stated) and include all randomised participants. Missing outcomes will be imputed using multiple imputation assuming the data is missing at random. Multiple imputed datasets will be created (n=50) and the imputation model will include baseline age, sex, and group, and the fully conditional specification logistic regression method will be used to impute the missing outcomes. The imputed datasets will be analysed using log-binomial regression and combined to output one inference. Adjusted analyses for potential covariates will be conducted if needed.

To check the robustness of the primary outcome the following sensitivity analyses will be conducted:

- self-reported continuous abstinence at 6 months (not biochemically verified)
- using the following varying cut-offs used for CO measurements: ≤ 3 ppm, ≤ 5 ppm, ≤ 8 ppm

The following sensitivity analyses will also be conducted for the primary outcome where groups will be compared using chi-squared tests:

- complete case analysis
- per protocol analyses where participants that have any major protocol violations will be excluded (see 6.2)
- assuming all missing outcomes are still smoking instead of using multiple imputation

Tests for heterogeneity will be used to examine if there is any difference in the groups on the unadjusted primary outcome for the following subgroups: baseline age (will be dichotomised based on the median), sex, ethnicity (Māori, non-Māori), education (< 12 years of attending school, 12 or more years of attending school), type of cigarettes smoked (RYO, factory made, both), AUDIT-C (low, high), cannabis use, motivation to quit, level of cigarette dependence (using HSI), and level of behavioural support received (will be categorised based on the data). Subgroup analyses will also be conducted by batch number of product received (Batch 1: early 2022, Batch 2: early 2023) to assess if there were any differences by batch.

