If the primary outcome is significant then cost analyses will be conducted. The cost per quitter, cost per person reducing their daily cigarette consumption and incremental cost-effectiveness ratio will be compared with New Zealand data from Quitline and other NRT service providers, and international studies, and will take a health sector perspective. However, the tobacco expenditure savings to individual smokers will also be calculated (for those who quit and cut down) to give a more societal perspective on the benefits. This calculation will use data on the daily amount smoked prior to quitting and the price of the particular products smoked. For those who cut down their consumption by a significant margin (i.e., 25% or more), the cost per person reducing their daily cigarette consumption will be calculated.

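### The sample size allows for multiple testing of the two primary comparisons, but the analysis section tests both at 5% without adjustment and gives no rule for a split result

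*SAP*

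**What the plan says.** Section 2.4 plans 800 participants (300 cytisine, 300 combination, 200 e-cigarette). It claims 90% power at two-sided 0.05 for a 13-point difference from cytisine and a 16-point difference from e-cigarettes, "taking account of multiple testing". It does not name the method of allowance or the alpha for each comparison.

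Section 7 states: "All statistical tests will be two-tailed and a 5% significance level throughout the analyses". It continues: "No adjustments for multiplicity are planned for any of the outcomes". It then says "All regression analyses will be conducted for the following two comparisons" and lists the same two comparisons; cytisine against e-cigarette is exploratory.

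Section 7.5 adds no exception, testing order or alpha split for the primary outcome. It says that "relative risks, absolute risk differences, and corresponding 95% confidence intervals will be calculated".

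Section 1 states two superiority hypotheses, one against each comparator, with no rule linking them. The one place where a significant primary result has a stated consequence is section 7.6: "If the primary outcome is significant then cost analyses will be conducted".

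**The concern.** The two sections describe different tests. Section 2.4 implies that the error rate across the two primary comparisons was limited when the trial was sized. Section 7 removes any such limit for every outcome, which includes the primary one, and gives no reason.

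Two things follow. First, if either comparison alone can support a claim for the combination, the chance of a false positive is larger than the allowance in 2.4 implies, and the power quoted there does not belong to the test in section 7. Second, the plan speaks of the primary outcome being significant although there are two primary comparisons. If one is significant and the other is not, a reader cannot tell whether that condition is met or whether the cost analyses, which section 4.2 lists as an outcome, will run. Settling this after the results are known would leave it open to a data-driven choice.

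**Working it through.** **Inputs, all from section 2.4.** Abstinence 25% (combination), 12% (cytisine), 9% (e-cigarette); 300/300/200 randomised; 28% loss; 90% power. Evaluable numbers: 300 × 0.72 = 216, 216, and 200 × 0.72 = 144.

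**Step 1: which alpha gives the stated 90%?** Two-sided test of two proportions with pooled variance under the null:

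power = Φ[(Δ − z·SE₀)/SE₁], with SE₀ from the pooled rate and SE₁ from the separate rates.

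Combination vs cytisine: Δ = 0.13, pooled rate 0.185.
- SE₀ = √(0.185 × 0.815 × 2/216) = 0.03736
- SE₁ = √((0.25 × 0.75 + 0.12 × 0.88)/216) = 0.03684
- At 0.05 (z = 1.960): (0.13 − 0.07323)/0.03684 = 1.541, power 93.8%
- At 0.025 (z = 2.241): (0.13 − 0.08375)/0.03684 = 1.256, power 89.5%

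Combination vs e-cigarette: Δ = 0.16, pooled rate (54 + 12.96)/360 = 0.186.
- SE₀ = √(0.186 × 0.814 × (1/216 + 1/144)) = 0.04186
- SE₁ = √(0.1875/216 + 0.0819/144) = 0.03791
- Power 98.0% at 0.05 and 96.0% at 0.025

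| Per-comparison alpha | vs cytisine | vs e-cigarette |
|---|---|---|
| 0.05 (section 7) | 93.8% | 98.0% |
| 0.0266 (Dunnett-type) | 90.0% | 96.2% |
| 0.0253 (Šidák) | 89.6% | 96.0% |
| 0.025 (Bonferroni, two tests) | 89.5% | 96.0% |
| 0.0167 (Bonferroni, three tests) | 86.5% | 94.3% |

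The stated 90% for the cytisine comparison is reproduced at a level corrected for two tests. The e-cigarette comparison exceeds 90% at every level, so it does not identify the alpha.

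**Step 2: number needed for 90% power, 25% vs 12%.**
- At 0.05: 186 evaluable per arm; 186/0.72 = 258.3, so 259 randomised
- At 0.025: 220 evaluable per arm; 220/0.72 = 305.6, so 306 randomised

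The plan has 300, which is close to 306 and well above 259.

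**Step 3: false positives when neither difference exists.** The combination arm is shared, so the two test statistics are correlated:

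ρ = (1/300)/√[(1/300 + 1/300)(1/300 + 1/200)] = 0.447.

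From the bivariate normal distribution:

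| Event | 0.05 each | 0.025 each |
|---|---|---|
| At least one significant, either direction | 9.2% | 4.7% |
| At least one falsely favouring the combination | 4.6% | 2.4% |
| Both falsely favouring the combination | 0.4% | 0.1% |

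Simulation with 216/216/144 and common rates from 9% to 25% gives 9.1% to 9.3% for the first cell.

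**Step 4: power under each possible rule.** One million simulated trials at 25/12/9% with 216/216/144 evaluable. Simulated single-comparison values run slightly above the formula values in step 1, so compare within this table.

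| Rule | vs cytisine | vs e-cigarette | Both | Exactly one |
|---|---|---|---|---|
| 0.05 each | 94.2% | 98.2% | 93.0% | 6.4% |
| 0.025 each | 90.0% | 96.3% | 87.8% | 10.7% |
| Holm | 93.8% | 97.5% | 92.8% | 5.8% |

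The last column is how often, at the planned rates, the trigger in section 7.6 would be undefined.

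**The case against.** The strongest reply is that unadjusted testing is a deliberate and defensible choice. Section 7 states the level, the sidedness, the two comparisons and the absence of adjustment. Section 1 poses two distinct questions, each with its own comparator, and many statisticians would not adjust across them. If both comparisons must succeed, no adjustment is needed either. This stands as a statement of what the sponsor could choose. The SAP argues neither position, however, and 2.4 says an allowance was made.

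A second reply is that the design alpha is not established. This stands in part:
- With a continuity correction the requirement is 280 per arm at 0.05 and 327 at 0.025, and neither is 300.
- If missing participants count as smokers, power against cytisine is 92.3% or 87.4%, and neither is 90%.
- The phrase in 2.4 could refer to power for both comparisons together, which is about 93% at unadjusted 0.05.

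A corrected alpha fits the stated 90% more closely than any of these, but it remains an inference.

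A third reply is that the harm is modest. That is fair. The 9.2% requires both nulls to be true and counts results against the combination. Each comparison keeps its own 5% error, and power under section 7 is higher than stated. The cost analyses are the only stated step that depends on a significant primary result.

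**Conclusion.** The point holds and should be fixed. Sections 2.4 and 7 conflict on multiplicity for the two primary comparisons, and the condition in 7.6 is undefined when they disagree.

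If either comparison suffices, the unadjusted plan has a 9.2% chance of at least one significant primary comparison under the global null, against 4.7% at 0.025 each; in the direction of the hypotheses it is 4.6% against 2.4%. At the planned rates, the comparisons disagree in about 6% of trials at 0.05. The issue is error control and interpretation; the trial is not too small.

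The figures rest on the rates and the 28% loss in 2.4, normal approximations, and 216/216/144 complete observations. Section 7.5 instead imputes missing outcomes for all randomised participants, so actual power will differ somewhat. The 0.025 level is inferred and needs the sponsor's confirmation.

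**What to change.** State one rule in section 7 before the outcome data are seen, and make 2.4, 7.5 and 7.6 agree with it. Any of these is coherent:

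1. **Adjust the two primary comparisons.** Exempt them from the no-adjustment statement and keep that statement for secondary and exploratory analyses. Either test each at 0.025 with 97.5% intervals, or use Holm (smaller p-value against 0.025, then the other against 0.05) and say that the 95% intervals in 7.5 are unadjusted and do not decide significance. State in 2.4 the per-comparison alpha that was used.
2. **Require both to be significant at 0.05.** Say so, explain that no adjustment is then needed, and give the power for both together (about 93%).
3. **Leave the tests unadjusted, with either one sufficing.** Delete the multiple-testing phrase from 2.4, restate power as about 94% and 98% at 0.05, and justify treating the two hypotheses as separate questions.

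Under any option, reword the condition in 7.6 to say whether at least one or both primary comparisons must be significant.

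Option 1 keeps closest to what 2.4 already says. The cost is wording only, with no more participants. Testing at 0.025 each widens intervals by about 14% (2.241/1.960 = 1.14) and lowers formula power from 93.8% and 98.0% to 89.5% and 96.0%. Holm costs less than one percentage point per comparison (94.2% to 93.8%, and 98.2% to 97.5%, simulated), but its decisions may not match the unadjusted 95% intervals.

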7.1. CONSORT flowchart

All participants who registered online for the trial will be accounted for and a CONSORT flow chart prepared as Figure 1 for the main paper. The reasons for non-participation will be discussed in relation to the external validity of the study and the pattern of protocol violations considered as potential sources of bias. Reasons for early withdrawal will be listed for all participants that prematurely discontinued their allocated intervention or the study. The number of participants that were registered but not randomised will also be presented.

7.2. Participant accountability

Tables describing patient accountability will be produced. The number of participants who were registered, fulfilled eligibility criterion, together with reasons for exclusion will be summarised. The status of participants at each follow-up visit, and the number of protocol violations will also be summarised.

7.3. Baseline characteristics

Baseline variables will be summarised for each intervention group. Since any differences between the groups at baseline could only have occurred by chance, no formal significance testing will be conducted.

7.4. Concomitant medications

Concomitant medications (coded to the Anatomical Therapeutic Chemical, ATC, classification system) by number of events and people will be summarised for each intervention group. Separate tables will be given for general ATC categories, and for the detailed ATC codes.

7.5. Primary outcome analysis

The proportion of participants that have been biochemically verified as continuously abstinent at six months by group will be analysed using log-binomial regression, and the risk in each group, relative risks, absolute risk differences, and corresponding 95% confidence intervals will be calculated. All analyses for the

primary outcome will be ITT (unless otherwise stated) and include all randomised participants. Missing outcomes will be imputed using multiple imputation assuming the data is missing at random. Multiple imputed datasets will be created (n=50) and the imputation model will include baseline age, sex, and group, and the fully conditional specification logistic regression method will be used to impute the missing outcomes. The imputed datasets will be analysed using log-binomial regression and combined to output one inference. Adjusted analyses for potential covariates will be conducted if needed.

To check the robustness of the primary outcome the following sensitivity analyses will be conducted:

- self-reported continuous abstinence at 6 months (not biochemically verified)
- using the following varying cut-offs used for CO measurements: ≤ 3 ppm, ≤ 5 ppm, ≤ 8 ppm

The following sensitivity analyses will also be conducted for the primary outcome where groups will be compared using chi-squared tests:

- complete case analysis
- per protocol analyses where participants that have any major protocol violations will be excluded (see 6.2)
- assuming all missing outcomes are still smoking instead of using multiple imputation

Tests for heterogeneity will be used to examine if there is any difference in the groups on the unadjusted primary outcome for the following subgroups: baseline age (will be dichotomised based on the median), sex, ethnicity (Māori, non-Māori), education (< 12 years of attending school, 12 or more years of attending school), type of cigarettes smoked (RYO, factory made, both), AUDIT-C (low, high), cannabis use, motivation to quit, level of cigarette dependence (using HSI), and level of behavioural support received (will be categorised based on the data). Subgroup analyses will also be conducted by batch number of product received (Batch 1: early 2022, Batch 2: early 2023) to assess if there were any differences by batch.

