Participants will be called on their quit date to verify they are quitting on that day (and to collect outcome data). If a participant states that they are not quitting on the scheduled 'quit date', they will be given one chance to reset their quit date within the next seven days, with this date becoming their new 'quit date' (which will trigger the scheduling of all subsequent follow-up calls). For participants who are unable to be contacted at quit date, their 'quit date' will be set in the system as six days after they received their courier pack (which will trigger the scheduling of all subsequent follow-up calls). Participants will be advised to continue with their allocated treatment irrespective of any lapses back to smoking.

Outcome assessments will be undertaken at one, three, and six months after the Quit date, and at 12 months in a subsample. At the six-month follow-up, in-person carbon monoxide tests will be performed for participants who live in the Auckland region to verify self-reported continuous smoking abstinence.

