4. STUDY OUTCOMES

4.1. Primary outcome

Verified six-month continuous abstinence (using Russell Standard) defined as self-report of smoking not more than five cigarettes from the Quit date and confirmed by an expired air carbon-monoxide (CO) measurement with a Bedfont Smokerlyzer (≤ 9 ppm signifying abstinence). Biochemical validation of self-reported cessation for Auckland participants will involve a researcher visiting participants within 72 hours if they claim to be abstinent, to obtain a CO reading. For participants outside of Auckland who self-report that they are smokefree, verbal consent will be sought from them to provide their contact details to their region's community-based smoking cessation service, so that they can undertake the CO monitoring within 72 hours. Sensitivity analysis will be undertaken looking at different cut-offs for the CO measurement, given lack of consensus about the best reading to use

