4.2. Secondary outcomes

The following secondary outcome measures will be collected over the phone on the quit date and at one, three, six and 12 months post-quit date:

- **Continuous abstinence** rates (using Russell standard) defined as self-report of smoking not more than five cigarettes in total from quit date (not collected at quit date)

Note if previous follow-up forms state they smoke more than 5 cigarettes since Quit date then subsequent follow-ups will be set to Not quit. Also, if a follow-up form is missing but the subsequent follow-up form(s) says they have smoked less than 5 cigarettes since Quit date (and no other previous follow-up forms have said they smoke more than 5 cigarettes since Quit date), then the missing follow-up form will have continuous abstinence set to 'Quit'.

- **Seven-day self-reported point prevalence abstinence** rates defined as no cigarettes, not even a single puff in the last seven days (not collected at quit date)
- **Change in average number of cigarettes smoked per day (CPD)** for participants still smoking
- **Proportion of participants who have significantly reduced smoking level** defined as reducing consumption by at least 25% (in terms of numbers of cigarettes per day)
- **Time to first lapse** (six and 12 months) defined as time to first cigarette smoked (even a single puff). From first follow-up form with question "Have you smoked any cigarettes at all in the last seven days, even a single puff?" equal to "Yes". Duration is calculated as the days since actual quit day to date of first lapse in the follow-up form.

Participants that withdraw will be censored on the last available visit, and participants that have not lapsed by the six (or 12) month follow-up will be censored on the six (or 12) months visit date. Note the first follow-up form with a lapse date will be taken since this will be more accurately remembered by participants than later visits.

- **Time to first relapse** defined as time to smoking more than five cigarettes a day for three or more days in a row. From first follow-up form with question “Have you smoked more than 5 cigarettes per day for 3 or more days in a row?” equal to “Yes”. Duration is calculated as the days since actual quit day to date of first relapse in the follow-up form

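### The primary imputation model uses only age, sex and group and leaves out the one- and three-month abstinence reports, and the SAP does not say whether an earlier reported failure settles the primary outcome

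*SAP*

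**What the plan says.** Section 7.5 imputes missing primary outcomes under missing at random, with 50 imputed datasets. The model is stated in full: "the imputation model will include baseline age, sex, and group, and the fully conditional specification logistic regression method will be used". The analysis includes all randomised participants and reports risks, relative risks and absolute differences.

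Section 4.1 defines the outcome as no more than five cigarettes from the quit date, "confirmed by an expired air carbon-monoxide (CO) measurement with a Bedfont Smokerlyzer".

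Section 4.2 lists the secondary measures, including self-reported continuous abstinence, as "collected over the phone on the quit date and at one, three, six and 12 months post-quit date" (continuous abstinence is not asked on the quit date itself). Under that secondary outcome it adds that "if previous follow-up forms state they smoke more than 5 cigarettes since Quit date then subsequent follow-ups will be set to Not quit". Neither 4.1 nor 7.5 repeats this rule or refers to it.

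Section 2.4 sets the scale of the missing data: "The sample size accounts for a 28% loss-to-follow-up at six months". Section 7.6 uses the same imputation method for the secondary abstinence and reduction outcomes.

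**The concern.** Because the outcome counts from the quit date, a participant who reports more than five cigarettes at month 1 or 3 has already failed. One who last reported abstinence at month 3 is far more likely than the arm average to be abstinent at month 6. The planned model uses neither fact. Missing at random must then hold given age, sex and arm alone, although relapse may well be related to loss.

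The effect depends on a point that the SAP leaves open:

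- **The section 4.2 rule does not reach the primary outcome.** Known failures can be imputed abstinent. If age and sex predict little, the result is close to complete case, so the planned complete-case analysis would not reveal the problem.
- **The rule does reach it.** Those still to be imputed are last-reported abstainers or people never reached. They are drawn at an overall arm rate, which is too low for the abstainers.

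At stake are the absolute risks, the risk difference and the precision of the primary analysis.

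**Working it through.** **Inputs from the SAP (2.4).** 300 randomised in each of the combination and cytisine arms; 25% and 12% abstinent; 28% lost, so 84 lost and 216 observed per arm if loss is equal.

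**The plan's own figure.** Pooled-variance power for 25% against 12% with 216 per arm, reading the allowance for multiple testing as two-sided 0.025 (my assumption):

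- SE under the null = √(2 × 0.185 × 0.815 / 216) = 0.0374
- SE under the alternative = √((0.25 × 0.75 + 0.12 × 0.88) / 216) = 0.0368
- Power = Φ((0.13 − 2.241 × 0.0374) / 0.0368) = 89.5%

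This reproduces the stated 90% (at 0.05 it would be 93.8%). The design therefore takes 28% loss as its working figure.

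**Assumptions not in the SAP.** Abstinent at 1/3/6 months: 45/33/25% (combination) and 28/18/12% (cytisine). 10% lost before month 1, regardless of status. Total loss 28% in each arm. After month 1, failures are lost 1, 2 or 3 times as fast as abstainers. Age and sex are uninformative, and every abstinence claimant is tested.

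**Formulas.** Let Y be the number observed abstinent at month 6 and K the number lost after reporting failure.

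- Planned model, rule not applied: Y / 216
- Rule applied, remainder drawn at the arm rate: Y / (216 + K)
- Reports used: each lost abstainer is imputed at the rate for the last report

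**Ratio 1, combination arm.**

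- Loss per interval after month 1: 1 − √(0.72/0.90) = 10.56%.
- Y = 216 × 0.25 = 54.
- K = 300 × 0.90 × 0.55 × 0.1056 + 300 × 0.90 × 0.8944 × 0.67 × 0.1056 = 15.7 + 17.1 = 32.8.
- Planned: 54/216 = 25.0%.
- Rule only: 54/248.8 = 21.7%.
- Reports used: 12.8 people lost after an abstinent month 1 contribute 12.8 × 25/45 = 7.1. The 8.4 lost after an abstinent month 3 contribute 8.4 × 25/33 = 6.4. The 30 never reached contribute 7.5. The total is 54 + 7.1 + 6.4 + 7.5 = 75, or 25.0%.

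In the cytisine arm, Y = 25.9 and K = 41.4, giving 12.0% as planned and 25.9/257.4 = 10.1% with the rule only.

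**All ratios** (combination / cytisine; differences and relative risks from unrounded rates):

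| Ratio | K | Planned, % | Difference | RR | Rule only, % | Difference | RR |
|---|---|---|---|---|---|---|---|
| 1 | 33 / 41 | 25.0 / 12.0 | 13.0 | 2.08 | 21.7 / 10.1 | 11.6 | 2.16 |
| 2 | 41 / 47 | 27.3 / 13.3 | 14.0 | 2.06 | 23.0 / 10.9 | 12.1 | 2.11 |
| 3 | 44 / 49 | 28.3 / 13.8 | 14.6 | 2.06 | 23.5 / 11.2 | 12.3 | 2.09 |

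The true values are 13.0 points and RR 2.08. Missing-equals-smoking (Y/300) gives differences of 9.4, 10.1 and 10.5.

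**Simulation** (1,500 trials per ratio, 50 imputations, same loss hazards in both arms, averaging 28%). The planned differences are 13.1, 13.9 and 14.0 (SE 3.69, 3.79, 3.83). With the reports used among those not already failed they are 13.0, 13.0 and 12.9 (SE 3.48, 3.39, 3.36). With no loss the SE is 3.12.

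**Other dropout patterns.** If abstainers are lost faster (ratio 0.5), the planned difference is about 12. In a second model, with 40% and 25% abstinent at the last interim report, loss was tied to relapse in the cytisine arm only. The planned difference was then 9.9, against 12.9 with full data and 12.9 with the report used.

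**The case against.** The best defence is that the section 4.2 rule already applies. The primary outcome is self-reported continuous abstinence plus CO confirmation, and someone set to not quit on self-report cannot be verified abstinent. On that reading the outcome is known, nothing is imputed, and only a cross-reference is missing. This is a fair reading. A reader might infer from section 7.5 that lost participants are imputed whatever they last reported, but the documents do not support that as a certainty. The defence does not rescue the model, though, because the rule alone gives 11.6 to 12.3 points.

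A reader might also count the known failures imputed abstinent (about 8 and 5 of the 84 lost per arm at ratio 1) as the bias. That is gross misallocation: at ratio 1 lost abstainers are under-imputed by the same amount and the net bias is zero.

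The shifts are also modest against an SE of about 3.7 points, rest on assumed trajectories and have no fixed sign. With equal 28% loss the relative risk barely moves without the rule, and a true null stays null when loss patterns are equal. All of this stands.

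The planned missing-equals-smoking analysis cannot make a reported failure abstinent, and the self-reported analysis carries the rule. Both show dependence on the assumption, but neither repairs the primary estimate.

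Finally, a reader might infer that abstinence claimants without a CO reading would be imputed as missing. The SAP does not code them expressly, but "confirmed by an expired air carbon-monoxide (CO) measurement with a Bedfont Smokerlyzer" in 4.1 and "The proportion of participants that have been biochemically verified as continuously abstinent at six months by group" in 7.5 point to counting them as not abstinent. That is no part of this point.

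**Conclusion.** The omission is a fact of the text and is worth correcting. It does not show that the primary comparison is misleading.

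Under the stated assumptions the planned difference is up to 1.6 points too high without the section 4.2 rule, or 0.7 to 1.4 points too low with the rule alone; it is about right when the reports are used. Other dropout patterns can reverse the first direction, and the larger distortion (9.9 against 12.9) needs loss to depend on relapse in one arm only. Under completely random loss, without the rule, the cost is precision alone: an SE of about 3.7 instead of 3.5 points.

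The figures are illustrations, not bounds. The SAP supplies only the sample sizes, the 25% and 12% rates and the 28% loss.

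**What to change.** In section 7.5, make two changes together, since the first alone pulls the difference down:

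1. Apply the section 4.2 rule to the primary outcome: anyone with an earlier report of more than five cigarettes since the quit date is set to not abstinent before imputation.
2. For participants not already failed and without a six-month report, add the one- and three-month continuous-abstinence reports to the imputation model, by arm. Handle perfect prediction, for example by imputing only among those not already failed.

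Use the same predictors for the imputed abstinence outcomes in section 7.6.

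The cost is SAP wording and modest programming, because the reports are already collected. The imputation model becomes slightly more complex. It still assumes missing at random given the reports, so the missing-equals-smoking analysis should be kept.
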